12.4 Direct Access To Source Data/Documents

Data generated by this study must be available for inspection by any regulatory authorities, by the Sponsor, DSMB, and the IRB as appropriate.

13 INVESTIGATOR REQUIREMENTS

13.1 Protocol Adherence

The investigator must adhere to the protocol as detailed in this document and agree that the Sponsor and the IRB must approve any change to the protocol. The investigator will be responsible for enrolling only those participants who have met the protocol screening and study entry criteria.

13.2 Case Report Forms

The CRFs will be used for the recording of all information and study data as specified by this protocol. The CRFs must be completed by the research personnel. The principal investigator is responsible for ensuring that accurate CRFs are completed in a timely manner.

13.3 Source Document Maintenance

Source documents are defined as the results of original observations and activities of a clinical investigation. Source documents may include, but are not limited to, study progress notes, e-mail correspondence, computer printouts, clinical laboratory data, and recorded data from automated instruments. All source documents produced in this study will be maintained by the investigator and made available for inspection by regulatory authorities. The original signed dated informed consent form for each participating participant shall be filed with records kept by the investigator and a copy given to the participant (parent or legal guardian, as appropriate).

The patient and parent-reported outcome questionnaires will be recorded directly on the paper forms and will be considered as source data.

13.4 Study Completion

Before a study can be considered completed or terminated, the investigator must have the following data and materials:

- Clinical laboratory findings, clinical data, and all special test results from screening through the EOT visit (to 30 days after the last dose of study agent).
- CRFs properly completed by appropriate study personnel and reviewed and approved by the investigator.
- Copies of protocol amendment(s) and IRB approval/notification if appropriate.
- A summary of the study prepared by the principal investigator (an IRB/IEC summary letter is acceptable).

13.5 Audits And Inspections

The principal investigator will permit study-related monitoring, audits, IRB review, and regulatory inspections by providing direct access to CRFs and source data/documents.

13.6 Institutional Review Board Approval

This protocol, the informed consent document, and all relevant supporting data must be submitted to the IRB for approval. IRB approval of the protocol, informed consent document, study materials and any advertisement

(if applicable) used to recruit study participants must be obtained before the study may be initiated.

The principal investigator (PI) is responsible for keeping the IRB advised of the progress of the study and of any changes made to the protocol as deemed appropriate, but in any case, at least once a year. The PI is also responsible for notifying the IRB of any unanticipated AEs that occur during the study in accordance with local IRB policies. Recent guidance from the USA FDA suggests that the following AEs should be reported to the IRB/IEC as “unanticipated problems:”

- Any AE that, even without detailed analysis, represents a serious unexpected AE that is rare in the absence of drug exposure (such as agranulocytosis, hepatic necrosis, Stevens-Johnson syndrome).
- A series of AEs that, on analysis, is both unanticipated and a problem for the study. There would be a determination that the series of AEs represents a signal that the AEs were not just isolated occurrences and were significant to the rights and welfare of participants.
- An AE that is described or addressed in the IB/package insert, protocol, or informed consent documents, or is expected to occur in study participants at an anticipated rate (e.g., expected progression of disease, occurrence of events consistent with background rate in participant population), but occurs at a greater frequency or at greater severity than expected.
- Any other AE that would cause the sponsor to modify the investigator brochure, study protocol, or informed consent form, or would prompt other action by the IRB to assure protection of human participants.

It will be the responsibility of the investigator to assure that the essential documents are available at the investigator site. Any or all of these documents may be subject to, and should be available for, audit by CCHMC or Sponsor auditor and inspection by the regulatory authorities as defined in the monitoring plan.

14 ETHICS

14.1 Ethics Review

The investigator will obtain approval to conduct the study from the appropriate regulatory agency in accordance with any applicable country and local-specific regulatory requirements prior to initiating the study.

14.2 Ethical Conduct Of The Study

This study will be conducted in compliance with the ethical principles of the Declaration of Helsinki, and any additional national or IRB-required procedures.

The investigator is responsible for ensuring that this protocol, the site’s informed consent form, and any other

information that will be presented to potential participants/parents or legal guardians (e.g. advertisements or information that supports or supplements the informed consent) are reviewed and approved by the IRB. The investigator agrees to allow the IRB direct access to all relevant documents. The IRB must be constituted in accordance with all applicable regulatory requirements. The investigator will provide the IRB with relevant document(s)/data that are needed for approval of the study.

14.3 Written Informed Consent And Assent

This study will be conducted in compliance with ICH E6 GCP: Consolidated Guidelines pertaining to informed consent and assent. At the first visit, prior to initiation of any study-related procedures, participants (parents or legal guardians, as appropriate) will give their written consent to participate in the study after having been informed about the nature and purpose of the study, participation/termination conditions, and risks and benefits. If the participant is unable to provide written informed consent, the participant's legally acceptable representative may provide written consent as approved by institutional specific guidelines. The informed consent document must be signed and dated by the participant, or the participant's legally authorized representative, prior to study participation. A copy of the informed consent document must be provided to the participant or the participant's legally authorized representative. Signed consent forms must remain in the participant's study file and be available for verification by the monitor, IRB, and/or regulatory authorities at any time. If participant's legally acceptable representative provides written consent, participants will also give their written assent to participate in the study, in accordance with institutional requirements.

15 DATA HANDLING AND RECORDKEEPING

15.1 Inspection Of Records

Data generated by this study must be available for inspection by any regulatory authorities, and by the IRB as appropriate. At a participant's/parent's or legal guardian's request, medical information may be given to his or her (child's) personal physician or other appropriate medical personnel responsible for his or her (child's) welfare. Participant medical information obtained during the course of this study is confidential and disclosure to third parties other than those noted above is prohibited.

15.2 Retention Of Records

The investigator shall retain records required to be maintained under this part for a period of 2 years.

15.3 Data Management

All study data will be collected via systems created in collaboration with the Data Management and Coordinating Center and will comply with all applicable guidelines regarding patient confidentiality and data integrity.

15.4 Registration

Registration of participants on this protocol will employ an interactive data system in which the clinical site will attest to the participant's eligibility as per protocol criteria and obtain appropriate informed consent. IRB approval for the protocol must be on file at the DMCC before accrual can occur from the clinical site.

The DMCC will use a system of coded identifiers to protect participant confidentiality and safety. Each participant enrolled will be assigned a local identifier by the enrollment site. This number can be a combination of the site identifier (location code) and a serial accession number. Only the registering site will have access to the linkage between this number and the personal identifier of the subject. When the participant is registered to participate in the study, using the DMCC provided web-based registration system, the system will assign a participant ID number. Thus each participant will have two codes: the local one that can be used by the registering site to obtain personal identifiers and a second code assigned by the DMCC. For all data transfers to the DMCC both numbers will be required to uniquely identify the subject. In this fashion, it is possible to protect against data keying errors, digit transposition or other mistakes when identifying a participant for data entry since the numbers should match to properly identify the participant. In this fashion, no personal identifiers would be accessible to the DMCC.

15.5 Data Entry

Data collection for this study will be accomplished with online electronic case report forms. Using encrypted communication links, on-line forms will be developed that contain the requisite data fields.

15.6 Data Quality and Monitoring Measures

As much as possible data quality is assessed at the data entry point using intelligent on-line data entry via visual basic designed screen forms. Data element constraints, whether independent range and/or format limitations or 'relative' referential integrity limitations, can be enforced by all methods employed for data input. QA reports assess data quality post-data entry. As we note, data quality begins with the design of the data collection forms and procedures and incorporates reasonable checks to minimize transcription and omission errors. Of the more important quality assurance measures are the internal validity checks for reasonableness and consistency.

- Data Monitoring: The DMCC identifies missing or unclear data and generates a data query to the consortium administrator contact.
- Data Delinquency Tracking: The DMCC will monitor data delinquency on an ongoing basis.

15.7 Laboratory Data Flow

The DMCC will provide laboratories with on-line forms and/or electronic data exchange mechanisms - depending on their capabilities and needs - to enter, update and obtain relevant data. On-line forms exist to verify specimen receipt, report specimen issues and submit test results for specimens. The preferred method to exchange data electronically is through the Specimen Management System Web Service. The Web Service allows laboratories to obtain specimen shipment information, receive individual specimens or specimen shipments, report specimen issues and communicate specimen aliquots in a secure manner (test result submission is planned). The DMCC will also support uploading of files electronically. All transactions are logged and validated for both methods.

1 INTRODUCTION

Pertaining to the objectives of the protocol, this statistical analysis plan (SAP) specifies, prior to finalization of study database, a comprehensive description of strategies and statistical techniques that are planned to assess clinical efficacy and safety of 1 food elimination (milk elimination alone, 1FED) versus 4 food elimination (milk, egg, wheat, and soy elimination, 4FED) diet intervention of Eosinophilic Esophagitis (EoE), and the following Glucocorticoids treatment.

The primary objective of this protocol is to conduct a prospective, non-blinded randomized trial comparing patient reported outcomes scores in novel empiric elimination dietary therapies in eosinophilic esophagitis (EoE) in order to assess the therapeutic viability of minimally restrictive empiric elimination diets as related to measures of patient's symptoms, quality of life, and pathology. The primary efficacy outcome will be the change in the standardized and validated Pediatric Eosinophilic Esophagitis Symptom Score v2 (PEESS).

Moreover, we also aim to assess the response to topical swallowed steroids in those who were non-responders to empiric dietary therapy regimens used during the initial phases of this study.

A variety of secondary endpoints, including pre- and post-therapy peak eosinophil counts per hpf and percentages of patients that attain histologic remission (<15 eosinophils/hpf), along with detailed histologic and endoscopic scores, novel biomarkers, and patient related outcome (PRO) measures will be analyzed between treatment groups.

In addition, we will assess the possible value of a variety of clinical characteristics and biomarkers in terms of predicting response to therapy. Relationship between PEES response and histologic response will be investigated as well to better understand PRO measures in predicting disease status.

2 STUDY DESIGN

This trial is comprised of 2 phases with each phase lasting 3 months. In the first phase, all participants will be randomized 1:1 to either 1FED or 4FED therapeutic diet. At the end of this phase, an EGD will be performed to assess histologic remission, which represents one of the primary current tools used in evaluating EoE disease activity during clinical trials and daily EoE care. Attainment of remission (esophageal eosinophil counts <15 eosinophils/high powered field) after Phase I will result in study discontinuation and maintenance of the “successful” dietary therapy. Dietary therapy non-responders who were on 4FED during Phase I will receive topical swallowed steroids for 3 months while on an unrestricted diet (Phase 2) followed by EGD with esophageal biopsies. Participants receiving SGC will return to an unrestricted diet (i.e. stop 4FED) prior to initiating SGC therapy. Dietary therapy non-responders who were on 1FED during Phase 1 will proceed to 4FED for 3 months (Phase 2) followed by EGD with esophageal biopsies.

3 STUDY OBJECTIVES

The purpose of this study is to evaluate the following objectives:

1.1 Primary Objective

To perform a prospective, randomized, non-blinded trial that determines patient reported outcomes scores

following 1FED (milk elimination alone) vs. 4FED (milk, egg, wheat, and soy avoidance) and their relative efficacy (Phase I).

- The primary endpoint for this study will be the change in PEES scores from baseline to post therapy assessed after the end of the 3 month Phase I.

1.2 Secondary Objectives

- To extend Phase I of this study with a prospective non-blinded trial that determines the rate of remission after treatment with 4FED (in participants failing 1FED in Phase I) or SGC (in participants failing 4FED in Phase I) (Phase II).
- To evaluate the effect of each therapy on histological remission (defined as a post therapy eosinophil count of <15 eosinophils/HPF) and by a variety of changes in eosinophils, including (a) pre- and post-therapy peak eosinophil counts; (b) partial remission (2-14 peak eosinophils/hpf); and (c) complete histological remission (≤ 1 peak eosinophils/hpf).
- To evaluate the effect of each therapy by utilizing the histology scoring system (HSS) created to express the severity and extent of other abnormalities in the gastrointestinal (GI) tract that often accompany eosinophilic inflammation.
- To determine the impact of each therapeutic intervention on biomarkers using the EoE Diagnostic Panel (EDP).
- To evaluate the clinical and psychosocial effect of each therapy using the Peds Quality of Life Inventory Eosinophilic Esophagitis Module (PedsQL EoE) to assess EoE symptoms and problems/feelings related to eating.
- To determine if any clinical parameters predict response to therapeutic intervention.
- To determine if any biomarkers including component-resolved diagnostics (CRD) [serum IgE component testing] predict response to therapeutic intervention.
- To determine if skin testing, in the form of prick and patch testing, predicts response to therapeutic intervention.
- Also to assess relationship between primary PEES score changes and histological scores (HSS).

4 STUDY PARTICIPANTS

4.1 Number of Participants

A total of 292 participants between the ages of 6-17 years were to be enrolled. Because of unexpectedly slow

enrollment, the actual number of participants will be around 50 total. The DMCC at the University of South Florida Health Informatics Institute will serve as the central data management center, with CCHMC serving as the primary site and the central IRB. Additional sites include: Children's Hospital of Colorado, Riley Hospital for Children, Children's Hospital of Philadelphia, University of California at San Diego/Rady Children's Hospital, Northwestern University/Lurie Children's Hospital, Tufts Medical Center, Mt. Sinai Kravis Children's Hospital, Arkansas Children's Hospital, and the University of North Carolina.

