12 STATISTICAL METHODS

12.1 Sample Size Calculation

Sample size was determined based on the primary endpoint of the trial: The overall PEES score change from pre-treatment. Based on a preliminary report¹⁸ we estimate that 40-50% of patients may respond to 1FED as our study is prospective compared with 65% response in this preliminary retrospective report and based on food reintroduction trial results³⁰. Likewise, we would expect 75% of patients to respond to 6FED based on the previously reported studies, and from this we extrapolated a projected response of 65% to 4FED, given that the 4 eliminated foods are consistently identified as the most common triggering antigens³⁰. As such, we estimate that 45% of patients will respond to 1FED and wish to detect an additional 20% increase for the 4FED (i.e. 65% response rate). A non-parametric Wilcoxon rank sum test will be applied for the primary efficacy endpoint comparison. We are assuming a difference in response rate of 45% vs 65% between the two treatment groups, and we further assume that those who respond to 1FED will naturally respond to 4FED. We also assume that those who responded will have a higher PEES score change than those who do not respond. Then the estimated probability of 4FED scores higher than 1FED is about 0.60 ($= 0.5 \times \text{prob. of response to both or neither} + 1.0 \times \text{incremental response rate from 1FED to 4FED}$). This will require 131 patients per group to reach 80% power at 0.05 test level. By accounting for a 10% early dropout rate, we propose a sample size of 146 per group, or 292 total patients to be enrolled.

12.2 Statistical Analyses: Aim 1

Demographic and patient characteristics will be summarized for the two treatment groups using mean \pm standard deviation or median [interquartile range] for continuous variables and frequency and percentages for categorical variables. Treatment comparisons will be performed using the two-sample t-test or Wilcoxon Rank sum test for continuous variables and the Fisher's Exact test for categorical variables. All tests will be conducted at $\alpha=0.05$, including the primary and secondary analyses.

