clustering within sites and will include the same covariates as for the primary analysis. The remission rate for non-responders who proceed to Phase II will be summarized separately depending on the treatment patients received during Phase I and Phase II. The 95% confidence interval for the rates will be provided.

12.3 Statistical Analyses: Aim 2

To evaluate the ability of biomarkers and phenotypic characteristics to predict response to therapeutic intervention, multivariable logistic regression analysis will be conducted with histological evaluation of remission/no remission as the dependent variable and biomarker levels as the independent variables. Multicollinearity of the independent variables will be assessed. The area under the receiver operating characteristic curve (AUROC) will be estimated along with 95% confidence interval. This analysis will be conducted based on the remission status at the end of Phase I. It will be repeated at the end of Phase II by including those patients who also responded to SGC.

A sample size of 292 total patients will provide at least 80% power to detect an AUROC of 0.60. This calculation is based on the assumption that 161 patients (66 1FED, 95 4FED) will be in remission at the end of Phase I (and therefore not move on to phase II) and 131 patients will not be in remission (with an estimated 10% dropping out and not continuing on to Phase II).

Additionally, a correlation analysis between PEES scores and biomarkers will be performed. Spearman's correlation coefficient and its confidence intervals will be computed to further assess predictive utility for the biomarkers of interest.

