6 STATISTICAL METHODS

6.1 Statistical Analyses: Aim 1

Demographic and patient characteristics will be summarized for the two treatment groups using mean \pm standard deviation or median [interquartile range] for continuous variables and frequency and percentages for categorical variables. Treatment comparisons will be performed using the two-sample t-test or Wilcoxon Rank sum test for continuous variables and the Fisher's Exact test for categorical variables. All tests will be conducted at $\alpha=0.05$, including the primary and secondary analyses.

There was going to be two sets of analysis populations in terms of efficacy assessment, the intent-to-treat and per protocol. However, since the total enrollment has been reduced to about 50, all patients randomized to Phase I of the study who have at least one clinical observation post randomization will be considered in intent-to-treat set. Only this set of population will be included in the statistical analyses. Originally, we plan to define patients who are at least 80% compliant to dietary assignment during Phase I, and who do not have any major protocol violations as in per protocol set. Now all analyses will be based on intent-to-treat population. Patients who do drop out of the trial before the end of Phase I will have their PEES done at the time of dropout. The primary endpoint is overall PEES score change from pre-treatment to the end of Phase I. If normality assumption is approximately valid, a linear mixed effect model will be applied to the primary efficacy variable,

account for site random effect, and other potentially important covariates, e.g. gender, race, and PPI use etc. Because of non-normal nature of the scores in previous research, a Wilcoxon rank sum test may be applied to compare between two treatment groups when normality is violated.

As a secondary endpoint analysis, remission rates (as defined by the percentage of participants achieving histologic remission (eosinophils less than 15/HPF) at the end of Phase I will be analyzed in the following 3 steps.

- (1) Remission rates will be computed along with their 95% CIs for each diet group separately;

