- (2) Remission rates will be compared between the two treatment groups using the generalized linear mixed effects model with the logit link (for binary outcome) that accounts for the clustering within sites. Important covariates will be analyzed in this model including gender, race, PPI use, atopy, age, and anthropomorphic features. Treatment group comparisons for secondary endpoints will be performed using the generalized linear mixed effects model using the link that is appropriate for the endpoint (i.e. logit for binary, log for Poisson count, identity for continuous). These models will account for the clustering within sites and will include the same covariates as for the primary analysis.
- (3) The remission rate for non-responders who proceed to Phase II will be summarized separately depending on the treatment patients received during Phase I and Phase II. The 95% confidence interval for the rates will also be provided.

6.2 Statistical Analyses: Aim 2

To evaluate the ability of biomarkers and phenotypic characteristics to predict response to therapeutic intervention, multivariable logistic regression analysis may be conducted with histological evaluation of remission/no remission as the dependent variable and biomarker levels as the independent variables. Multicollinearity of the independent variables will be assessed. The area under the receiver operating characteristic curve (AUROC) will be estimated along with 95% confidence interval. This analysis will be conducted based on the remission status at the end of Phase I. It may also be repeated at the end of Phase II by including those patients who also responded to SGC.

Additionally, a correlation analysis between PEES scores and biomarkers will be performed. Spearman's correlation coefficient and its confidence intervals will be computed to further assess predictive utility for the biomarkers of interest.

Missing data will be handled in the following manner. For the primary efficacy measure of PEES, each patient is expected to complete the questionnaire; even if the patient terminates participation early (dropout) for any reason. The total PEES score is the average of 20 item scores, as long as there are at least 10 item response non-missing, as described previously. No imputation of missing total PEES will be performed. The early dropout reasons will be recorded, and rates will be assessed between treatment groups for potential patterns.

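### Enrolment falls to around 50, but the primary PEES comparison has no restated power (about 21–23% for the Wilcoxon test, against the planned 80%) and no named confidence interval

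*SAP*

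**What the plan says.** - **Planned size and power.** Protocol 12.1 assumes response rates of 45% on 1FED and 65% on 4FED, and derives a probability of about 0.60 that a 4FED score change exceeds a 1FED one. It then states: "This will require 131 patients per group to reach 80% power at 0.05 test level". Allowing for 10% dropout gives 146 per group and 292 in total. Protocol 12.3 has a second figure: at least 80% power for an AUROC of 0.60 with 292 patients.
- **Current size.** SAP 4.1 says that "the actual number of participants will be around 50 total" and gives slow enrolment as the reason.
- **Primary test.** SAP 6.1 applies alpha 0.05 to all tests, "including the primary and secondary analyses". The first choice is a linear mixed model with a random site effect and covariates. If the scores are not normal, "a Wilcoxon rank sum test may be applied to compare between two treatment groups when normality is violated".
- **Changes the SAP ties to the smaller sample.** There are two. The per-protocol set is dropped ("However, since the total enrollment has been reduced to about 50"), and tests of treatment-effect heterogeneity are called exploratory (end of SAP 6.2).
- **Intervals named.** For remission, "Remission rates will be computed along with their 95% CIs for each diet group separately". Intervals are also named for Phase II remission rates, the AUROC and Spearman's correlation. None is named for the difference in PEES change between the diets, in SAP 6.1 or in Protocol 12.2.

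**The concern.** The only power stated for the primary comparison belongs to a trial more than five times the size now expected (292/50 = 5.8). The SAP was written with the shortfall known and adapts to it in two places, but it leaves the inferential status and precision of the primary result unaddressed.

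Protocol 6.5.1.1 hypothesises that 4FED is more effective than 1FED on PEES. If the planned effect is real, a non-significant result is still the likely outcome at this size. If the Wilcoxon route is taken as written, the report could consist of a p-value alone. A reader could not then see that the data fit both the planned benefit and an advantage for 1FED. Protocol 3.2 adds to the risk of misreading, because it says as background that a comparable response with fewer foods removed would be an important advance.

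**Working it through.** **Inputs.** P(4FED>1FED) = 0.5 × (0.45 + 0.35) + 1.0 × 0.20 = 0.60; alpha 0.05; power 80%; dropout 10% (all Protocol 12.1). Allocation is 1:1 (SAP 2). N is about 50 (SAP 4.1). Sidedness is not stated and is inferred in step 1.

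**1. Reproduce the protocol's figure.** Noether's formula for the Wilcoxon test with equal groups is N = (z₁₋α/₂ + z_power)² / [12 × 0.25 × (P − 0.5)²].
- Two-sided: (1.96 + 0.8416)² / (3 × 0.01) = 261.6, so 131 per group. Then 131/0.9 = 145.6, so 146 per group and 292 in total. This matches.
- One-sided: 206.1, so 104 per group. This does not match, so two-sided is taken.

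**2. Power at the current size.** Power = Φ(√(3N) × 0.10 − 1.96).

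| N evaluable | Power | P needed for 80% power, 0.5 + 2.8016/√(3N) |
|---|---|---|
| 262 | 80% | 0.60 |
| 60 | 27% | 0.71 |
| 50 | Φ(1.225 − 1.96) = 23% | 0.73 |
| 45 (50 less 10%) | Φ(1.162 − 1.96) = 21% | 0.74 |
| 40 | 19% | 0.76 |

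A finite-sample standard error, √[(n₁+n₂+1)/(12n₁n₂)], gives 22.7% at 25 per group and 20.9% at 22.5. Simulating the protocol's responder model (65% against 45%, every responder ranked above every non-responder) gives about 22% at 25 per group and about 81% at 131.

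**3. If normality holds.** P = 0.60 corresponds to d = √2 × z(0.60) = 0.358 SD. An unadjusted two-group comparison at 25 per group has about 24% power. Its 95% CI half-width is t(0.975, 48) × √(2/25) = 0.57 SD, which is wider than the effect.

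**4. Covariate adjustment.** The documents give no SD, correlation or explained variance. As an illustration only, assume the covariates explain a share R² of the variance, so that d becomes 0.358/√(1 − R²). At 25 per group, power is about 32% for R² = 0.3 and about 42% for R² = 0.5.

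**5. Precision of an estimate of P = 0.60 (Hanley–McNeil).** Variance = [P(1−P) + (n−1)(P/(2−P) − P²) + (n−1)(2P²/(1+P) − P²)] / n².
- 25 per group: (0.24 + 24 × 0.0686 + 24 × 0.09)/625 = 0.00647; half-width 1.96 × 0.0805 = 0.158; interval 0.44 to 0.76.
- 131 per group: half-width 0.068; interval 0.53 to 0.67.

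In the simulation, the estimate points towards 1FED in 11% of trials at 25 per group and in 0.2% at 131.

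**6. AUROC figure.** The same formula with Protocol 12.3's split of 161 in remission and 131 not has c(1−c) = 161 × 131/292² = 0.2474. It gives Φ(√(12 × 0.2474 × 292) × 0.10 − 1.96) = 84% at 292. With the same split at N = 50 it gives Φ(1.218 − 1.96) = 23%. This figure has not been updated either.

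**The case against.** The best reply is that nothing is hidden. The SAP reports the shortfall openly, does not repeat the 80%, and the protocol ties that figure to 131 per group. The sample size was set by circumstance, and the first-choice mixed model yields an estimate and standard error anyway. The closing paragraphs of SAP 6.2 also say that treatment-effect estimates will be extracted from the primary and secondary analyses. All of this is true. What remains is that the estimate sentence sits in the heterogeneity paragraph, names no interval, and supplies no estimator for the Wilcoxon route. SAP 6.1 itself says earlier scores were non-normal, so that route is a realistic one.

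Four stronger readings are tempting, and the documents do not support them:

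- *The SAP cut the trial.* It reports an enrolment shortfall, not a redesign.
- *The primary analysis was left untouched.* Under Protocol 12.2 the per-protocol set could trigger a second primary analysis, so dropping it does alter the primary analysis. The gap is in inferential status and precision.
- *The Aim 2 regression was softened because of the small sample.* Protocol 12.3 says "multivariable logistic regression analysis will be conducted with histological evaluation" and SAP 6.2 says "multivariable logistic regression analysis may be conducted with histological evaluation", but the SAP gives no reason for the change.
- *The plan would read a null result as support for 1FED.* No statistical section says so. The hypothesis is superiority of 4FED, and the sentence in Protocol 3.2 is background.

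**Conclusion.** The point holds, and the plan should be fixed. The protocol's 131 per group is correct on its inputs, so this is a figure overtaken by events and not an arithmetic error. At around 50 enrolled, Wilcoxon power for the protocol's own effect is about 21–23% (19–27% for 40 to 60 evaluable), so a real effect of the planned size would be missed in more than three trials out of four. The result rests on P = 0.60, on two-sided testing (inferred, because only that reproduces 131), and on equal groups. It applies to the Wilcoxon test and, at about 24%, to an unadjusted normal comparison. A reader might take 23% as the power of the first-choice mixed model, but the documents do not allow that to be computed. Under the illustrative R² values above it stays well below 80%.

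The power sentence corrects the record. The missing estimator and interval for the Wilcoxon fallback matter more, because they determine what the trial can conclude.

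**What to change.** Add two statements to the SAP.

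(a) In SAP 4.1: *The protocol's 80% power figures (primary PEES and AUROC) applied to 292 patients and do not apply at the current size. With about 50 enrolled (about 22–25 evaluable per group), a two-sided 0.05 Wilcoxon test has about 21–23% power for P(4FED>1FED)=0.60, and 80% power needs P of about 0.73–0.74. Covariate adjustment in the mixed model may change this.*

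(b) In SAP 6.1: *The primary PEES difference will be reported as an estimate with a 95% CI (model-based if the mixed model is used; Hodges–Lehmann shift or P(4FED>1FED) if the Wilcoxon test is used), and a non-significant result will not be read as evidence that the diets are similar.*

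The cost is a few lines of text and one confidence interval. No patients are added and no test changes. The drawback is that the stated power becomes less favourable.
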